Private Health Information	PHI
Rapid Eye Movement	REM
Same Day Surgery	SDS
Shriners Hospitals for Children	SHC
Standard Operating Procedure	SOP
Statistical Analysis Software	SAS
Total Sleep Time	TST
Wake After Sleep Onset	WASO

[figure not shown]
Table of Contents

	Study Summary
	Study Schema
1.0	Introduction
2.0	Objectives
3.0	Subject Selection
4.0	Study Design
5.0	Subject Safety
6.0	Data Handling and Record Keeping
7.0	Quality Control and Quality Assurance
8.0	Statistical Considerations
9.0	Study Finance
10.0	References

STUDY SUMMARY

Title	The Effectiveness of Healing Touch on Sleep, Pain, Anxiety, Anesthesia Emergence, Satisfaction and Cost of Care
Population:	5-25 years; admitted for an elective surgery procedure
Number of Subjects	200
Study Duration	Study duration is from approximately 9 pm (when the electrodes are applied for the sleep test) the evening prior to surgery through no more than 8 hours after surgery the following day.
Study site(s)	Shriners Hospital for Children, Cincinnati
Objectives	
We hope to learn the following:
 
 • Determine if Healing Touch improves the quality and quantity of patient sleep the night before surgery • Define any side effects associated with Healing Touch • Establish the value of Healing Touch on the patient's pain, stress, anxiety and recovery from anesthesia. • Determine if Healing Touch is associated with measures of patient satisfaction and cost of care.
Statistical Methodology	Bivariate comparisons will be used to evaluate differences in baseline variables between Healing Touch and control groups (ex. age, gender and race, also type of surgical procedure e.g. burn versus other reconstructive procedure). These latter variables are potential covariates for secondary analysis. Analysis of variance (ANOVA) or Kruskal-Wallis test and Chi-square analysis will be used for these comparisons. Similarly, the association between outcome variables and baseline variables will be examined; correlation and ANOVA or Kruskal-Wallis will be used as appropriate.

Sleep 7 – Study Design Schematic

Media Resources Diagram May 2014, Revised March 2015

1.0

Introduction

1.1 Background

Tension between art and science is fueling insurgency against mainstream medicine as the general public, patients, caregivers and health care professionals alike are integrating complementary and alternative medicine (CAM) into wellness routines and treatment practices with increased frequency.¹ From acupuncture to zinc, the portfolio of CAM options is blossoming as evidenced by the formation of the National Center for Complementary and Integrative Health (NCCIH) within the National Institutes of Health (NIH).² Energy medicine is one of five domains of CAM recognized by NCCAM.³ It is based on the concept that there is universal energy, the human energy field is subject to imbalances, and a therapist can re-pattern the disrupted field by using compassionate intent to channel healing energy into a person to improve health.

Energy-derived healing such as healing touch (HT) is based on principles of quantum physics that humans are energetic organisms that occupy a physical space.⁴ We create heat, generate electricity and even have a measurable magnetic field. Many integrative medicine practitioners believe that we have specific energy vortices that control the flow of subtle energy in the body (referred to as chakras) and that energy travels through the body along vertical pathways called meridians. Layers of energy within and surrounding the body are important for health and well-being. Disease and injury are believed to be related to disturbances in the chakras, meridians and energy fields.⁵⁻¹⁰ In theory, HT uses noninvasive hand techniques to balance human and environmental energy disturbances, remove biofield blockages, restore innate healing forces and reactivate the mind-body-spirit connection.^{6,7,9,10}

Bioenergy healing is controversial. Whereas the art of HT has long been established, only recently has science begun to explore the bioenergy healing realm; hence definitive proof of its clinical value is sparse. There is however, good scientific evidence to indicate that bioenergy fields exist.^{4,5,11} Yet neither the ability to manipulate these energies by thought or intention, nor the existence of chakras and meridians have been conclusively proven. This lack of knowledge makes it difficult for professionals to respond to the voluminous testimonials of success. Without evidence that either supports or refutes the benefit(s) of energy medicine, health fraud and quackery will prevail. The problem is serious. Unproven remedies may be harmful and waste money, and using ineffective practices may prevent people from getting necessary medical treatment.

[figure not shown]
The clinical efficacy of HT within conventional medical science appears to be in 5 main areas: reduction of anxiety/improvement in mood/well-being,¹²⁻²⁰ relief of pain,^{15,16,19-24} hastening of wound healing,²⁵⁻²⁷ immune modulation^{28,29} and improvement of sleep.^{20,22,30,31} Much of the research demonstrating benefit has employed observational approaches (qualitative studies, case studies or patient satisfaction measures) rather than experimental design. However a few rigorous studies exist, such as the randomized trial²⁰ that demonstrated burn patients receiving HT compared to sham treatment had reduced pain scores after 5 days of treatment.

Whereas estimated incidence of insomnia in the general population is 10 to 20%,³⁹ sleep deprivation is present in nearly every critically ill burn patient⁴⁰

and ranges between 20 – 40% in children multiple years following injury.^{31,41-43} The cause of pervasive degradation of sleep quantity and quality in acutely injured patients is multifactorial, including nocturnal treatment interruptions and medication side effects.^{33-35,41,43-50} Physiologic deterrents to sleep include the wound itself and the metabolic response to injury and infection.⁴⁴⁻⁵³ Psychological stress such as pain and anxiety disturb sleep.⁵⁴⁻⁵⁷ Sounds associated with patient care, monitoring equipment, infusion pumps, phones, pagers, television and conversation as well as room light interfere with sleep and body rhythms normally entrained by daylight and darkness.^{44,46,47,49-74} More difficult to explain is the finding that sleep disruption continues post discharge, long after the wound has healed.^{31,41-43,75-79} The chronic nature of postburn and/or postsurgical dyssomnia is unsettling in view of its insidious effects on quality of life, wound healing and health. Experts in sleep medicine have also demonstrated significant psychological consequences of sustained sleep inadequacy and sleep fragmentation. Sleep disturbances predispose individuals, especially children, to heightened anxiety, attention-deficit hyperactivity disorder, impaired memory, reduced cognition and poor social integration.⁸⁰⁻⁸⁵

Sleep deficiency is of concern because insufficient restorative sleep is an added stressor to the patient and may be a potential impediment to recovery.^{46,86} Achieving adequate sleep represents an unmet need during hospitalization. We speculate that re-establishing normal sleep patterns will help to accelerate patient recovery from the metabolic and psychological abnormalities commonly associated with surgery and ultimately improve well-being. The significance of this study is that it will establish the efficacy of HT as a therapeutic intervention for improving sleep in hospitalized children during the perioperative period as well as characterize electroencephalographic energetics associated with HT using a prospective, randomized blinded design.

Because clinical and pharmacological modulation of postburn sleep disturbance has been largely ineffective,^{32-38,87,88} we explored the utility of HT as a potential sleep intervention. The investigation involved 10 children undergoing burn reconstructive care.³¹ Patients were studied an average of 7.2 ± 2 years postburn. Subjects were randomized to HT versus no HT treatment using a 2 period crossover design. Data revealed that HT had a significant effect on both the quantity and quality of sleep. Total sleep time (TST), sleep efficiency, stage 2 sleep (N2) and number of REM periods were significantly enhanced with HT. The percent of time asleep increased during the first 7 hours, which suggests that HT had an extended effect on the parameters being examined beyond that incurred during the HT procedure. Findings of remarkable HT benefit³¹ provide the impetus for this follow-up confirmation study.

EFFECT OF HEALING TOUCH ON SLEEP

VARIABLE	HEALING TOUCH NIGHT N=10	NON-HEALING TOUCH NIGHT N=10	p-value
Total sleep time	391 (251, 476)	331 (268, 373)	.02
Sleep efficiency	76 (53, 90)	66 (55, 78)	.04
Sleep latency	8.4 (2.8, 34.9)	17.2 (13.5, 48.0)	.20
Awakenings	32 (25, 38)	30 (23, 32)	.42
Wake after sleep onset	99 (46, 210)	107 (53, 194)	.77
REM periods	4.5 (2.0, 5.0)	3.5 (2.0, 4.0)	.03
N1 minutes	26 (21, 32)	28 (18, 30)	.83
N2 minutes	213 (136, 236)	160 (107, 204)	.03
N3 minutes	63 (29, 93)	34 (8, 120)	1.0
REM minutes	83 (62, 91)	60 (40, 86)	.20
N1 % norm	212 (174, 241)	304 (197, 531)	.11
N2 % norm	110 (103, 136)	123 (85, 132)	.23
N3 % norm	67 (44, 110)	49 (31, 125)	.43
REM % norm	95 (82, 101)	86 (47, 116)	.73
Efficiency % norm	80 (56, 94)	69 (58, 83)	.04

Data shown as median (25th, 75th percentile)

Taken together, our extensive prior work characterizes significant dyssomnia following injury. Sleep disturbances are long term in nature with widespread health implications for children recovering from burns. Compared with a normal population, seriously burned patients (both acute and rehab/outpatients) demonstrate significant sleep disturbance manifested by decreased total sleep time, frequent arousals, impaired sleep efficiency, nightmares and deficient stages of 3+4 and REM sleep. The pathophysiology underlying postburn sleep deprivation is clearly multifaceted and has not been fully elucidated. Our investigations have led to breakthrough preliminary findings demonstrating the possible clinical efficacy of HT as a sleep intervention.³¹

1.2 Rationale and Risks/Benefit

1.2.1 Rationale: Our work is unique because no one has ever related electroencephalography (EEG) recordings of energy to HT. Healing touch may prove useful in the treatment of refractory sleep disorders common during recovery and could lead to widespread application worldwide in terms of its development as a safe, economical and non-invasive procedure that promotes sleep, physiological restoration and psychological well-being. Such findings would dovetail nicely with the Affordable Care Act as America transitions to value based care, requiring the adoption of therapies that emphasize lower costs and improved quality of life.

1.2.2 Risks/Benefit: This study involves no more than minimal risk. There may not be direct benefit noted for study subjects; information from this study may influence the care of surgical populations in the future. This information is communicated to participants/consenting parents/legal guardians upon study introduction and is noted upon consent. The risks of this study are minimal; however, the potential for HT therapy to promote sleep and improve postoperative morbidity in elective surgery populations is novel and significant.

2.0 Objectives:

There is a fundamental gap in understanding how the energy-based, CAM approach of HT can be used to maximize health and improve recovery following disease or injury. Whereas the art of HT has long been established, there has been a recent explosion in its integration as a therapeutic intervention. However, proof of its mechanistic action and clinical value is lacking. Our long-term goal is to expand the capacity for improved

medical care and enhanced quality of life of children and young adults in alignment with the Affordable Care Act which emphasizes value and reduced health care spending. The objective of this study is to develop foundational scientific evidence that validates efficacy of a standardized HT intervention designed to promote sleep, a proven integral component of repair and recovery. These data are critical to advance the science and practice of HT, ultimately providing understanding of how this type of CAM can make a positive contribution to patient care. Our central hypothesis for this investigation is that HT generates improvement in a recipient's sleep in association with electroencephalographic changes. We formulated this hypothesis on the basis of strong preliminary data demonstrating that HT has a positive impact on PSG outcomes. We further postulate that HT and its associated increase in restorative sleep will benefit common sources of preoperative stress and/or postoperative anguish (e.g. anesthesia emergence, pain, anxiety, nausea). With recognition that well-designed clinical trials of HT are sparse; secondary objectives of this application are to produce cost to benefit information and to determine if patient satisfaction is enhanced by the addition of HT.

- 2.1 The *primary objective* of this study is (Aim 1) to determine the safety and efficacy of healing touch intervention on improving measures of sleep.

With recognition that our original work demonstrating deficits in sleep and quality of life outcomes in hospitalized children, this prospective randomized trial will examine a new method for improving sleep. We postulate that HT will safely modulate changes that favor enhanced restorative sleep outcomes measured by PSG variables such as total sleep time (TST), sleep efficiency, sleep stages and time awake after sleep onset (WASO).

- 2.2 A *secondary objective* of this study is to establish the value of HT on perioperative management of surgery-related outcomes (Aim 2).

The intent of this aim is to evaluate the impact of HT on distress preceding surgery as measured by anxiety, pain, and laboratory indices of stress. This investigative aim will also assess the effectiveness of HT postoperatively in management of anesthesia emergence, sedation, anxiety, and pain reflected by clinical, psychometric and medication measures of well-being as well as track the incidence of postoperative nausea/vomiting. Upon completion of this study objective, it is expected that important information will be provided that determines whether HT intervention can mediate clinical improvement and comfort measures.

- 2.3 An additional secondary objective is to examine measures of patient satisfaction and cost of care associated with HT (Aim 3). There is a need to ensure the value of healthcare services. Therefore, in addition to safety/efficacy considerations, additional key determinants of quality-based surgical care include patient satisfaction and financial outcomes. We will connect satisfaction and cost findings to clinical outcomes, with the goal of providing an objective interpretation of benefits and costs. These essential steps will justify (or contest) the value of HT services within the framework of perioperative clinical practices.

- 2.4 The rationale of selection of outcome measures (sleep, surgery- related outcomes, patient satisfaction and cost of care) is that Healing Touch is expected to provide an inexpensive, non-invasive method that will prosper as a safe and efficacious adjunctive preoperative treatment.

3.0 Subject Selection:

- 3.1 Inclusion Criteria
 - 3.1.1 5 years to 25 years of age
 - 3.1.2 Scheduled for an elective operative procedure
 - 3.1.3 Written informed consent and HIPAA release signed by parent or legal guardian; assent as appropriate
- 3.2 Exclusion Criteria
 - 3.2.1 History of anoxic or suspected brain injury
 - 3.2.2 History of head injury within the last year
 - 3.2.3 Face/head phenomena that prevents proper placement of PSG leads
 - 3.2.4 No informed consent or HIPAA release
- 3.3 Inclusion of Gender and Minorities
 - 3.3.1 Entry into this study is open to patients of both genders and all ethnic backgrounds.
- 3.4 Subject Recruitment, Enrollment and Consent Process
 - 3.4.1 Study specific recruitment cards, a 1 page flyer and also a patient education brochure describing healing touch will be used for marketing. Patients requiring surgery will be invited to participate by receiving recruitment information in person and/or via a mailing of related study materials to their home. Before surgery, a staff member from Patient Access may encourage patient or caregiver to look for study information when they receive their study packet mailing (per script). This will occur during the normal preoperative phone call. In addition, a study co-investigator may contact patients or caregivers) per script who are identified as potential candidates. Once study information has been reviewed by the patient/family, and the patient/family is agreeable to participate in the study, a study co-investigator will work with scheduling personnel to plan research admission the evening before elective surgery.
 - 3.4.2 Informed consent will be obtained from the participants and/or their legal guardians by trained staff authorized to consent for this study.
 - 3.4.2.1 The conversation is expected to include a thorough discussion of what is expected to happen during the study, risks and benefits of the planned therapy, and any possible alternatives.
 - 3.4.2.2 The family will be given a copy of the signed consent form.
 - 3.4.2.3 For participants who are less than 18 years of age, some of these participants are able to give assent and others are too young. If it is determined that a participant is able to give assent (generally children 11 years or older), the consenting staff will attempt to explain the study at both the participant's and the legal guardian's comprehension level.

4.0 Study Design/Procedures:

- 4.1 General Design
 - 4.1.1 Elective surgery patients will be prospectively assigned to treatment group using single blinded stratified randomization. A cross-over trial was considered but because our prior work suggests that HT has an extended carryover and thus an effect on outcome,³¹ we felt this would not be an appropriate approach. If HT is performed before the non-HT period, there could be residual HT effects manifested during the non-intervention period.

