4.2 Study Procedures

PSG will be performed the night before surgery. PSG (Sandman ELITE Sleep System, Natus Medical Inc, Buffalo NY) will include simultaneous nocturnal recording of EEG, electromyogram (EMG), electrooculogram (EOG), respiration, heart rate, oxygen saturation, video and audio recordings and body movement in 30-second epochs. Subjects will be connected to PSG at approximately 2100 with recordings from approximately 2200 until 0600 the following morning (unless patient has an early surgery time). Soft music will play for approximately 60 minutes in all groups after the sleep machine is turned on.

In an effort to assure concealment of group allocation during scoring of the sleep data, scoring will be delayed for approximately one month following study intervention. In addition, the video will be turned off during the first hour of

scoring performed by the registered sleep technologist. The American Academy of Sleep Medicine's (AASM) newly released guidelines, The AASM Manual for the Scoring of Sleep and Associated Events: Rules, Terminology and Technical Specifications⁹⁸ will be used for scoring and interpretation of sleep stages. PSG provides comprehensive summary reports of sleep stages and also generates sleep latency, TST, WASO, arousals and sleep efficiency measures. [name] MD, Director of the CCHMC's Hospital Sleep Disorders Center and board-certified sleep specialist, blinded to experimental conditions, will perform the specialized data interpretation. A copy of the sleep test report will be provided to study participants.

Patients will have vital signs (temperature, respiration, heart rate, blood pressure) assessed prior to the sleep study and repeated preoperatively (the morning of surgery). Vital signs and vomiting will be assessed in the operating room. Vital signs, and pain score (using an observational scale⁹⁹ [OPAS] and/or numeric rating [1-10 scale] as appropriate) will be assessed post-operatively both upon arrival to the post-anesthesia care unit (PACU) and before PACU discharge. Vital signs, and pain score will also be recorded upon arrival to post-recovery patient room and at discharge. Nausea and vomiting will be assessed in the PACU and in the post-recovery patient room. Minutes in the OR, PACU and patient room (time from arrival until discharge) will be recorded.

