Laboratory parameters (C-reactive protein, glucose, cortisol and D25) will be obtained (from approximately 5 mL of blood) in the operating room. Since there is a strong argument that HT reduces stress and anxiety, the results of this study could provide data demonstrating improved hormonal balance following HT intervention. There also exist reports linking sleep with metabolism of glucose and vitamin D.

An anxiety test (Yale Preoperative Anxiety Scale) will be obtained preoperatively (in patient unit prior to preoperative meds and repeated in the preoperative surgery area).¹⁰⁰ Anesthesia emergence score, sedation score and nausea and vomiting will be assessed in the PACU.¹⁰¹⁻¹⁰³ Incidence of nausea and vomiting in the post recovery patient room (on the floor) will also be recorded.

A patient satisfaction survey will be administered post recovery that includes questions specific to the HT procedure, sleep and also includes four questions identical to that contained in Press Ganey Pediatric Inpatient survey (questions B5, D4, K3 and I9; <http://www.pressganey.com/>) to assess contentment with overall inpatient care.

Implicit in the definition of economic consequences of healing touch, we will also collect select utilization and cost outcome measures including total charges from admission to study discharge as well as charges specific to the Post Anesthesia Recovery Room. Labor cost of HT, length of stay in recovery room (number of minutes), length of hospital stay (number of hours) and medications administered for sleep, anxiety, pain, itch, nausea, vomiting and anesthetics during the defined study period all have high cost implications and thus will be examined as well.

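### Aim 2 names pain before surgery and anxiety after surgery as outcomes, but section 4.2 schedules no preoperative pain score and no postoperative anxiety scale

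*Combined protocol and SAP*

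**What the plan says.** Section 2.2 splits Aim 2 into two periods. Before surgery, the aim is to "evaluate the impact of HT on distress preceding surgery as measured by anxiety, pain, and laboratory indices of stress". After surgery, it is to "assess the effectiveness of HT postoperatively in management of anesthesia emergence, sedation, anxiety, and pain", with postoperative nausea and vomiting tracked as well.

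Section 4.2 sets the assessment times:

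- **Before surgery, general checks:** "Patients will have vital signs (temperature, respiration, heart rate, blood pressure) assessed prior to the sleep study and repeated preoperatively (the morning of surgery". No pain score is named at either check.
- **Pain score (OPAS and/or numeric rating), together with vital signs:** these "will be assessed post-operatively both upon arrival to the post-anesthesia care unit (PACU) and before PACU discharge". Later, "Vital signs, and pain score will also be recorded upon arrival to post-recovery patient room and at discharge".
- **Anxiety (Yale Preoperative Anxiety Scale):** it "will be obtained preoperatively (in patient unit prior to preoperative meds and repeated in the preoperative surgery area".
- **PACU scales:** emergence, sedation, and nausea and vomiting. No anxiety scale is among them.
- **Medication:** drugs given for anxiety and pain, among others, are recorded over the study period. They are listed with the utilization and cost measures.

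Section 8.3.2 plans to model Aim 2 outcomes from baseline to after recovery, adjusting change for baseline and testing the time-by-group interaction. Section 8.3.1 says that the same repeated-measures approach will be used for the anxiety and pain scales. Section 6.1 points to the study procedures as the place where the collected variables are detailed.

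**The concern.** A site that follows section 4.2 to the letter takes no pain score before surgery and no anxiety rating after it. Each score exists on one side of the operation only, while both the objective and the analysis model call for both sides. Perioperative scores that are not taken at the time cannot be recovered later, so the mismatch has to be settled before data are collected.

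At stake is a stated part of a secondary aim. Without a preoperative pain score, the trial has no direct evidence on whether Healing Touch eases pain before surgery. Without a statement of what represents anxiety after surgery, that component has no defined endpoint, and the analyst would have to choose one after the fact.

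**Working it through.** The point rests on no numerical figure in the plan, so the check is to set the objective beside the schedule.

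| Item in 2.2 | Period | Direct measure scheduled in 4.2 |
|---|---|---|
| Anxiety | before | Yes: anxiety scale, 2 times |
| Pain | before | **None** |
| Laboratory indices | before | Yes: one blood sample in the operating room |
| Anesthesia emergence | after | Yes: PACU |
| Sedation | after | Yes: PACU |
| Anxiety | after | **No scale**; medication use only |
| Pain | after | Yes: pain score, 4 times |
| Nausea/vomiting | after | Yes: PACU and patient room |

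There are 3 + 5 = 8 items, and 8 − 2 = 6 have a direct measure.

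**Times by side of surgery.** Pain score: 0 before, 4 after (PACU arrival, before PACU discharge, arrival in the patient room, discharge). Anxiety scale: 2 before, 0 after.

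**What this means for 8.3.2.** A baseline-adjusted change from before surgery to after recovery needs at least one score on each side. Pain lacks the earlier one and anxiety the later one, so neither can enter that model. Group comparisons across the four postoperative pain scores, or across the two preoperative anxiety scores, remain possible.

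**What medication records can add.** Section 4.1.2 runs the study period from about 9 pm the evening before surgery to 8 hours after it, or to earlier discharge. Anxiety medication is therefore recorded after surgery. The same record also includes drugs given before surgery, and 4.2 defines no postoperative part. For preoperative pain, analgesic use before surgery would be a weak proxy, and the preoperative sentence of 2.2 does not offer medication as a measure.

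**Side check on the power statements in 8.3.2.** With power ≈ Φ(d√(n/2) − z), where z = 2.409 for two-sided alpha 0.016:

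- Pain: d = 0.4/0.52 = 0.769, n = 48 per group. 0.769 × 4.899 − 2.409 = 1.36, so power is 91.3% (90.3% by the t-test), consistent with the stated 80% or more.
- Anxiety: d = 0.7, n = 50 per group. 0.7 × 5 − 2.409 = 1.09, so power is 86.2% (85.1% by the t-test), matching the stated 85%. At the printed alpha of 0.16 it would be about 98%, so 0.16 looks like a misprint of 0.016.

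Both figures fit a comparison of scores that are scheduled, namely postoperative pain and preoperative anxiety. They neither cause nor cure the mismatch.

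**The case against.** The strongest reply concerns anxiety. Section 2.2 goes on to say that the postoperative outcomes are "anesthesia emergence, sedation, anxiety, and pain reflected by clinical, psychometric and medication measures of well-being". Medication is thus a measure type that the aim itself accepts, and anxiety medication is recorded until 8 hours after surgery. Nor does the sentence promise a separate psychometric scale for each of its four outcomes. This stands. A reader might infer from the schedule that postoperative anxiety has no data in any arm, or that both components cannot be answered at all. The documents do not support that: anxiety after surgery has an indirect measure. What remains is that no scale is scheduled and no endpoint is defined from the medication record.

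A second reply is that not everything is visible. The procedure diagram in 4.1.3 is not shown, the items on the preoperative data collection form named in 6.4.3 are not given, and 6.4.2 lists pain scores from the medical record without limiting them to after surgery. This limits certainty: a preoperative pain score may be taken in practice. It does not remove the point, because 6.1 refers the reader to the study procedures and 4.2 lists the pain and anxiety times without these two.

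A third reply is that the sentence in 8.3.2 on change over time is generic and makes no specific claim about preoperative pain or postoperative anxiety. That is fair, and it is why the text needs a statement of which outcomes the model covers. With 8.3.1 extending the approach to the anxiety and pain scales, a reader would otherwise assume that both are included.

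**Conclusion.** The mismatch between sections 2.2, 4.2 and 8.3.2 is real on the visible text. Preoperative pain has no direct measure. Postoperative anxiety rests at most on medication use. The baseline-to-recovery analysis cannot be run on the pain score or the anxiety scale as scheduled.

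The size is two of eight outcome-by-period items in one secondary aim. The primary polysomnography endpoints, the sample size, the postoperative pain comparison and the preoperative anxiety comparison are untouched.

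The conclusion assumes that 4.2 is the full list of scheduled scores. If the diagram or the preoperative form includes a pain score, the defect becomes one of wording, but 4.2 would still need to say so. The change should be made because it is cheap and lets the trial answer a part of Aim 2 that it has already stated.

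**What to change.** 1. **Pain.** In 4.2, add the pain score already in use (OPAS and/or numeric rating) to the existing vital-sign checks before the sleep study and on the morning of surgery. The first gives a baseline and the second a preoperative value after the intervention. This is 2 extra scores per subject, or 400 over 200 subjects, at contacts that already take place: a minute or two per subject.
2. **Anxiety.** In 2.2 and 8.3.2, state that the anxiety scale addresses preoperative anxiety only, that postoperative anxiety is assessed through anxiety medication given after surgery, and that no pre-to-post change analysis will be run on the scale. This is a wording change, on the assumption that medication records carry times that separate doses before and after surgery. A new postoperative rating is not proposed: the only anxiety instrument in the plan is a preoperative one, and choosing another for ages 5 to 25 is a larger task.
3. **If the pain score is not added,** delete pain from the preoperative half of 2.2 and exclude it from the baseline-adjusted pre-to-post analysis in 8.3.2. This costs only the wording, but that part of the aim is given up.
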